4.3 Patient Disposition

Counts and percentages of patients who complete the study and who withdraw from the study, with the reason for withdrawal, will be presented. For the patients who withdraw early from the study or who are excluded from certain populations, reasons for withdrawal or exclusion, and the last date of study participation will be listed. Patient enrollment and disposition will also be provided by site.

4.4 Protocol Deviations

All protocol deviations information including patient ID, date /visit (if applicable), and the type of deviations will be listed. Deviations will further be categorized as major and minor based on the following definitions.

A major protocol deviation will be defined as failure to adhere to the protocol, study specific

CONFIDENTIAL:

This document and its contents are the property of Gala Therapeutics, Inc. Any use, reproduction or distribution without the written permission of Gala Therapeutics, Inc. is prohibited.

	TYPE: Clinical Trial Document	Document No:	CLN-0000X
	TITLE: CS003 Statistical Analysis Plan	Revision:	A
		Release Date:	
		DCN	Page 7 of 44

procedures or clinical investigation plan requirements which could impact the rights, safety or welfare of the patients and/or the completeness, accuracy and integrity of the study data. Examples include failure to obtain signed consent prior to trial treatment, enrolled patient not meeting eligibility criteria, or breach of patient confidentiality.

A minor protocol deviation will be defined as a divergence from approved study design or study which does not affect the patient’s rights, safety, or welfare, and/or the completeness, accuracy, and integrity of the study data. Examples include patient visit outside the scheduled follow-up window, or test not completed per protocol.

Protocol deviations will be categorized based on deviation type (e.g., visit performed out of window, missed visit) and deviation category (minor or major). The number of occurrences and percent of patients experiencing each category of deviation will be reported.

4.5 Demographic and Baseline Characteristics

Descriptive summaries of demographic and baseline characteristics will be presented. If multiple assessments for a given variable are available, Baseline measurements refer to the last measurement collected prior to the index procedure visit (Visit #2).

Demographic and baseline characteristics include age, gender, race, weight, height, smoking history (pack-years), GOLD stage and other measures of respiratory status, COPD medications, quality of life (CAT and SGRQ), and body mass index (BMI). Continuous variables (e.g., age, weight, BMI) will be summarized by patient count, mean, standard deviation (SD), median, inter-quartile range (IQR), minimum, and maximum. Categorical variables (e.g., race, gender) will be summarized by the number and percentage of patients in the corresponding categories.

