6.0 SUBJECT ELIGIBILITY

6.1 Inclusion Criteria

6.1.1 Subject is at least 40 years of age.

6.1.2 Subject has had chronic bronchitis for a minimum of two years, where chronic bronchitis is defined clinically as chronic productive cough for three months in each of two successive years in a patient in whom other causes of productive cough have been excluded.

6.1.3 Subject's responses to the first two questions of the COPD Assessment Test (CAT) must sum to at least 7 points. If the sum of the first two CAT questions is 6 points and the subject's total CAT score is greater than 20 points, the

subject may be enrolled. The first two questions of the CAT questionnaire are as follows:

"For each item below, place a mark (X) in the box that best describes you currently."

I never cough	 0	 1	 2	 3	 4	 5	I cough all the time
I have no phlegm (mucus) in my chest at all	 0	 1	 2	 3	 4	 5	My chest is completely full of phlegm (mucus)

- 6.1.4 Subject has a pre-procedure post-bronchodilator FEV₁ percent predicted of greater than or equal to 30% and less than or equal to 80% within three months of enrollment.
- 6.1.5 Subject has had 1 or more COPD exacerbations, defined as an acute worsening in respiratory symptoms that requires additional treatment, in the 12-months prior to enrollment
- 6.1.6 Subject has a SGRQ score of greater than or equal to 25 and CAT score of greater than or equal to 10.
- 6.1.7 Subject has a cigarette smoking history of at least ten packs years.
- 6.1.8 Subject is, in the opinion of the principal investigator, able to adhere to and undergo two bronchoscopies.
- 6.1.9 Subject has provided signed informed consent.
- 6.2 Exclusion Criteria
 - 6.2.1 Subject has lower respiratory tract infection (e.g., pneumonia, mycobacterium avium-intracellulare infection (MAI), tuberculosis, or severe COPD exacerbation (as defined per GOLD 2018 guidelines¹⁸) within the six weeks prior to the initial treatment bronchoscopy or mild or moderate COPD exacerbation (per GOLD guidelines) within 4 weeks of the procedure.
 - 6.2.2 Subject is taking > 10 mg of prednisolone or prednisone per day.
 - 6.2.3 Subject has an implantable cardioverter defibrillator or pacemaker.

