7.2 Description of Visits

7.2.1 Visit #1. Screening and Enrollment

Subjects who meet the eligibility criteria and have signed an informed consent form may be enrolled in the study. Assessments performed exclusively to determine eligibility for this study will be done only after obtaining signed informed consent from the subject. Assessment performed for clinical indications (i.e., not exclusively to determine study eligibility) may be used for screening evaluation even if the studies were completed before informed consent was obtained.

All screening procedures must be completed within 90 days prior to start of study treatment.

Note: If the subject experiences a COPD exacerbation or other change in functional status between screening and the first bronchoscopy, screening procedures should be repeated as appropriate at the investigator's discretion. Refer to the Table 7.1 Schedule of Events for listing of required screening procedures.

General Screening Notes:

High Resolution CT Scan

High resolution computed tomography (HRCT) is incorporated as a tool to define subject inclusion criteria and to assess post treatment changes. CT acquisition will be per the CT Core Manual provided separately to each site upon completion of training by the designated CT core lab for this study.

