7.2.9 Visit # 9 Phone Call Visit (10 months post Bronchoscopy # 2)

The study coordinator / research nurse calls the subject on the telephone 10 months \pm 2 weeks. Any adverse events or changes in medication are reported accordingly. A study visit may be scheduled if clinically warranted.

7.2.10 Visits # 10, 11, 12, 13 and 14 In-office Follow-up Visits (Annual Follow-up post Bronchoscopy # 2)

Subjects will return for follow-up visits at 12 months \pm 4 weeks after Bronchoscopy #2 (Visit 4) and annually thereafter for 5 years (\pm 4 weeks). Refer to the Schedule of Events table for a complete listing of required tests.

Note: If the subject experiences a COPD exacerbation or other change in functional status within 6 weeks of any scheduled follow-up visit, the investigator should consider rescheduling study follow-up visits based on his or her best medical judgement to allow for a true assessment of the patient's stable condition once the subjects symptoms have returned to normal. It is recommended that subjects return to clinical baseline for a minimum of two-weeks prior to undergoing study specific follow-up testing.

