4.9.4.1 Responder Rates

The proportion of patients meeting the following improvement thresholds at follow-up will be summarized:

- at least 2-point decrease (improvement) in CAT total score
- at least 4-point decrease (improvement) in CAT total score
- at least 2-point decrease in the sum of the first two questions of the CAT

CONFIDENTIAL:

This document and its contents are the property of Gala Therapeutics, Inc. Any use, reproduction or distribution without the written permission of Gala Therapeutics, Inc. is prohibited.

	TYPE: Clinical Trial Document	Document No:	CLN-0000X
	TITLE: CS003 Statistical Analysis Plan	Revision:	A
		Release Date:	
		DCN	Page 11 of 44

- at least 2-point decrease in CAT total score and a 1-point decrease in either of the first two questions of the CAT
- at least 4-point decrease (improvement) in SGRQ total score
- at least 8-point decrease (improvement) in SGRQ total score

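### The baseline CAT and SGRQ scores are by default the screening scores that qualified the patient, so change from baseline leans modestly toward improvement

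*SAP*

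**What the plan says.** **Schedule.** Table 7.1 has the CAT and SGRQ at screening (Visit 1) and not at Visit 2. They come next before bronchoscopy at Visit 4, then at 3 and 6 months and at the annual visits.

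**Baseline.** SAP 4.5, for variables with more than one assessment: "Baseline measurements refer to the last measurement collected prior to the index procedure visit (Visit #2".

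**Entry.** Protocol 6.1.3: "responses to the first two questions of the COPD Assessment Test (CAT) must sum to at least 7 points". A sum of 6 is also admitted if the total CAT exceeds 20. Protocol 6.1.6: "Subject has a SGRQ score of greater than or equal to 25 and CAT score of greater than or equal to 10".

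**Timing and stability before treatment.** Protocol 7.2.1: "All screening procedures must be completed within 90 days prior to start of study treatment". After an exacerbation or other change in functional status between screening and the first bronchoscopy, "screening procedures should be repeated as appropriate at the investigator's discretion". Exclusion 6.2.1 bars a severe exacerbation in the six weeks, or a mild or moderate one in the four weeks, before the procedure.

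**Stability at follow-up.** The note after Protocol 7.2.10, repeated below Table 7.1, asks the investigator to consider rescheduling when an exacerbation or functional change falls within six weeks of a visit. It adds: "It is recommended that subjects return to clinical baseline for a minimum of two-weeks prior to undergoing study specific follow-up testing".

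**Use of the scores.** Changes in SGRQ and CAT at 6 and 12 months are secondary outcomes, with sign-test p-values (SAP 4.9.1 and 4.9.2). One responder criterion in SAP 4.9.4.1 is "at least 2-point decrease in the sum of the first two questions of the CAT".

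**The concern.** The measurement that admits the patient is also the measurement from which change is counted. Part of a high qualifying score is chance, and that part does not recur, so the average change is negative (improvement) even if the device does nothing. The two-item CAT responder criterion is the most exposed, because it reuses the items that carry the tightest entry threshold.

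A second mechanism runs the same way. The intervals in 6.2.1 count back from the procedure, not from the questionnaire, so a score taken during or just after an exacerbation can stand as baseline. The discretionary repeat in 7.2.1 has no criterion for return to a stable state. Follow-up testing does have one, though only as a recommendation.

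At stake is how the uncontrolled SGRQ and CAT changes, the responder rates and the p-values are read.

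**Working it through.** The plan has no effect-size or power figure to reproduce. The documents give no screening means, SDs or test-retest reliability, so those inputs are assumptions and ranges are shown.

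**1. Windows (protocol figures).** Days of the 90-day screening window that lie outside the 6.2.1 intervals:
- mild or moderate exacerbation: 90 - 28 = 62 days (69%)
- severe exacerbation: 90 - 42 = 48 days (53%)

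On those days a questionnaire could be completed during an exacerbation and the patient still be eligible, if screening is not repeated.

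**2. Regression to the mean, one threshold at a time.** Expected fall = (1 - rho) x SD x phi(a) / (1 - Phi(a)), with a = (cut - mean) / SD.
- SGRQ, cut 25, mean 45, SD 20, rho 0.7: a = -1; 0.3 x 20 x 0.242 / 0.841 = 1.73 points. Over means 35 to 55, SDs 15 to 20 and rho 0.7 to 0.9: 0.1 to 3.1 points.
- Two-item CAT, cut 6.5 (whole-number score of 7 or more), mean 7, SD 2, rho 0.7: a = -0.25; 0.3 x 2 x 0.387 / 0.599 = 0.39 point. Over means 5 to 7 and rho 0.6 to 0.9: 0.1 to 1.1 points.

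**3. Two-item CAT sum, full 6.1.3 rule, no device effect (simulation).** Screened mean 6 to 7.5, SD 1.5 to 2.5, ICC 0.6 to 0.9; other CAT items mean 13, SD 6.

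| | Screening score as baseline | Separate pre-treatment baseline |
|---|---|---|
| Mean drift, range | about -0.1 to -0.8 | about 0 |
| 2-point responders, range | about 2% to 36% | about 2% to 23% |
| Middle case (mean 7, SD 2, ICC 0.7) | -0.34; 20% | 0; 15% |

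The middle-case excess is 5 percentage points, or 0.05 x 30 = 1.5 patients in 30. Without the sum-of-6 route it would be -0.41 and 21%. A repeat run gave a top value of 35% rather than 36%, so the range ends are approximate.

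**4. Total scores, joint entry rule of 6.1.3 and 6.1.6, no device effect (simulation).** Two-item mean 6 to 7, SD 2; other CAT items mean 13, SD 6; SGRQ mean 45, SD 17; correlation 0.5 between true scores and 0.3 between errors; rho 0.7 to 0.9. The sign test at n = 30 needs 21 in one direction (p = 0.043).

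| | Screening baseline | Separate baseline |
|---|---|---|
| CAT drift | -0.3 to -1.3 | about 0 |
| SGRQ drift | -0.5 to -1.9 | about 0 |
| CAT responders, 2 points | 34.7% to 48.2% | 31.1% to 38.7% |
| SGRQ responders, 4 points | 32.2% to 43.4% | 29.9% to 38.1% |
| False sign-test improvement, CAT | 4.5% to 14.1% | 1.4% to 1.6% |
| False sign-test improvement, SGRQ | 4.1% to 7.6% | 2.0% to 2.2% |

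Within scenarios, the responder rate rises by about 4 to 10 percentage points (CAT) and 2 to 5 (SGRQ). The nominal one-direction error is 2.5%.

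**5. Unstable screening scores.** Added drift = share unstable x excess points. For SGRQ, 0.1 x 4 = 0.4 up to 0.3 x 12 = 3.6 points. Nothing in the documents fixes the share or the excess, so this shows only how the term scales.

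**The case against.** A reader might infer that the plan has no stability rule before treatment. It does not go that far. The 7.2.1 repeat is triggered by any change in functional status as well as by an exacerbation, and a repeated score becomes the baseline under SAP 4.5. A patient screened while unwell who then recovers has arguably had such a change. Exclusion 6.2.1 also secures an exacerbation-free run-up to the procedure. What stands is narrower: neither provision requires stability on the day of the baseline questionnaire, the repeat is left to discretion, and an exacerbation just before screening is not clearly covered.

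A reader might also infer that follow-up scores are taken only in a stable state. The protocol says only that rescheduling should be considered and that two weeks is recommended. Both sides are discretionary, so the asymmetry is one of degree.

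The consequences are also limited. The endpoints are unpowered and mainly descriptive, the sign tests are labelled exploratory, and the open single-arm design is stated. All of that is correct. It lowers the weight of the point without removing a bias of known direction that is cheap to avoid.

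Finally, SAP 4.9.4.5 already judges the data on several optional measures insufficient, so collection was evidently well advanced and a new Visit 2 questionnaire may come too late for most patients. That is fair, and it is why the fix has two parts.

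**Conclusion.** The point holds as a modest bias toward improvement that a single-arm design cannot separate from a device effect. Its existence and direction follow from Table 7.1, Protocol 6.1 and SAP 4.5. Its size rests on assumed means, SDs and reliabilities.

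Under the joint entry rule, the selection drift in the totals stays below the 2-point CAT and 4-point SGRQ thresholds. It is also small beside the first-in-human changes of about 8 and nearly 20 points (Protocol 1.3). It would be wrong to infer that this artefact could account for changes of that size. It matters more for proportions and p-values: in some scenarios the responder rates and the chance of a false sign-test improvement rise appreciably. The instability part could add to the drift, but the documents do not allow it to be sized. The change is worth making; it is not an error that invalidates the study.

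**What to change.** **Patients not yet treated.** Add the CAT and SGRQ before bronchoscopy at Visit 2 in Table 7.1, as is already done at Visit 4. Reword SAP 4.5 so that baseline is the last measurement before the index procedure. The present sentence is tied to the visit and would exclude a score taken at Visit 2. The new baseline would be separate from the qualifying score, and the 6.2.1 intervals would then run up to it.

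**Patients already treated.** Add a sensitivity analysis that excludes screening scores taken within six weeks after a recorded exacerbation. Six weeks is the protocol's own follow-up window, and exacerbation history is collected from Visit 1. This addresses instability but not regression to the mean. The report should therefore also carry a stated regression-to-the-mean caveat on the SGRQ and CAT changes and on the two-item CAT responder rate.

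**Cost.** Two short questionnaires per patient at an existing visit, one schedule edit, one SAP sentence and one extra analysis. The reported improvement may be slightly smaller.

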4.6 Device Performance

Device performance will be assessed through an analysis of device malfunctions, the duration of the procedure in minutes (bronchoscope insertion to removal), device time in minutes (RheOx catheter insertion to removal), the number of device activations, and the post procedure hospital stay. Device performance will be summarized descriptively using counts, mean, SD, median, IQR, minimum and maximum where applicable.

4.7 Prior and Concomitant Medications

Prior and concomitant medications will be categorized using the World Health Organization (WHO) Drug Dictionary and listed. In addition, COPD related medications (i.e., long acting

CONFIDENTIAL:

This document and its contents are the property of Gala Therapeutics, Inc. Any use, reproduction or distribution without the written permission of Gala Therapeutics, Inc. is prohibited.

	TYPE: Clinical Trial Document	Document No:	CLN-0000X
	TITLE: CS003 Statistical Analysis Plan	Revision:	A
		Release Date:	
		DCN	Page 8 of 44

beta and muscarinic antagonists, inhaled corticosteroids) will be summarized at baseline and follow-up to assess the impact on study outcomes of any changes in medical management over the course of the study.

4.8 Safety Analyses

Treatment emergent AEs and SAEs will be summarized and listed. Treatment emergent AEs (TEAE) are defined as those adverse events occurring during or after bronchoscopy #1 (Visit 2). No inferential statistical testing of the safety data will be conducted.

4.8.1 Serious Adverse Events of Interest

The primary safety analysis is the incidence of treatment emergent serious adverse events of interest through 12 months. Serious adverse events of interest are defined in the study protocol and in Section 3.2.1 above.

The count and percent of patients experiencing each of the events listed in Section 3.2.1 above and a composite summary of patients experiencing any of these events through the 12-month visit will be summarized. Events will also be summarized within discrete time periods (as described in section below) from bronchoscopy #1 (Visit #2) through 12 months in order to assess the procedure effect.

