4 STATISTICAL METHODOLOGY

4.1 Sample Size Determination

Since this is an early feasibility study, no formal sample size calculations were conducted. Up to 30 patients will be enrolled and treated with the study device to assess the effect of the investigational device in the target population. This sample size was based upon clinical judgement rather than statistical considerations.

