4.9.1 St. George's Respiratory Questionnaire (SGRQ)

SGRQ total score and changes from baseline will be summarized by scheduled time point using descriptive statistics. The mean, standard deviation (SD), median, and inter-quartile range (IQR) will be reported. Statistical testing to evaluate change from baseline using methods consistent with the statistical assumptions required to support the analyses may also be conducted for exploratory purposes. P-values from a Sign test corresponding to non-parametric approach to test whether the median differs from zero and confidence intervals will be reported.

CONFIDENTIAL:

This document and its contents are the property of Gala Therapeutics, Inc. Any use, reproduction or distribution without the written permission of Gala Therapeutics, Inc. is prohibited.

	TYPE: Clinical Trial Document	Document No:	CLN-0000X
	TITLE: CS003 Statistical Analysis Plan	Revision:	A
		Release Date:	
		DCN	Page 10 of 44

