5.2 Handling of Missing Data

Patient compliance with required follow up will be tabulated and reported as described in section 4.3. All analyses (tables and figures) will be conducted using all available data. No imputation or other evaluation of missing data will be performed.

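### The primary 12-month composite of serious adverse events is planned as a count and percent, with no confidence interval and no defined 12-month N

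*SAP*

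**What the plan says.** SAP 4.8.1 states: "The primary safety analysis is the incidence of treatment emergent serious adverse events of interest through 12 months". For the components it plans "The count and percent of patients experiencing each of the events listed in Section 3.2.1 above"; for the composite, "a composite summary of patients experiencing any of these events through the 12-month visit will be summarized". No interval, time-to-event estimate or patient-year rate is named for either. SAP 4.8 adds: "No inferential statistical testing of the safety data will be conducted".

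Table 14.3.1 follows the text. Each component row shows patients, percent and number of events. The row headed Total is blank and is not defined as patients with any event. Each column has its own N, which no footnote explains. The 12-month total column covers Bronchial Rheoplasty 1 through 12 months after Bronchial Rheoplasty 2.

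Three other parts of the SAP bear on the denominator and on precision:

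- **Population.** SAP 4.2.1 bases every analysis on patients with at least one RheOx treatment, and SAP 4.1 says "Up to 30 patients will be enrolled and treated with the study device".
- **Missing data.** SAP 5.2 uses whatever data are available and says "No imputation or other evaluation of missing data will be performed".
- **Other endpoints.** For change in SGRQ (4.9.1), CAT (4.9.2) and the other endpoints (4.9.4), p-values and "confidence intervals will be reported". Hospitalizations (4.9.3) and COPD exacerbations (4.8.2.1) also get rates per patient-year.

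**The concern.** Safety is the primary objective, yet its headline result is the one for which the plan gives neither a measure of precision nor an adjustment for length of follow-up. Secondary and exploratory endpoints get one or the other. In Table 14.3.1 itself, the hospitalization rows carry a patient-year rate and the primary events above them do not.

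The sample size was set by clinical judgement, so nothing elsewhere in the plan tells a reader what event risk 30 patients can exclude. A reported zero, or a very low percentage, may then be taken as stronger evidence of safety than it is. Without a defined N, even the percentage is not fully prespecified: the same count can be divided by all treated patients or by those still in follow-up.

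**Working it through.** **Inputs.** The maximum of 30 patients is from SAP 4.1. Neither document gives an expected event risk, a dropout rate or a precision target, so there is no planned figure to reproduce. The risks and dropout rates below are assumptions for illustration.

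**Step 1: what 30 patients can exclude.** Exact (Clopper-Pearson) 95% limits for x events in n patients are the 2.5% quantile of Beta(x, n−x+1) and the 97.5% quantile of Beta(x+1, n−x). For x = 0 the upper limit reduces to 1 − 0.025^(1/n); with n = 30 this is 11.6%.

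| Events | Percent | Exact 95% interval |
|---|---|---|
| 0/30 | 0.0% | 0 to 11.6% |
| 1/30 | 3.3% | 0.1 to 17.2% |
| 2/30 | 6.7% | 0.8 to 22.1% |
| 3/30 | 10.0% | 2.1 to 26.5% |
| 6/30 | 20.0% | 7.7 to 38.6% |

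Put the other way, a true risk of 5% gives no events in 30 patients with probability 0.95^30 = 21.5%.

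**Step 2: early exits, if N is all treated patients.** Let R be the true risk over the window and D the dropout proportion, with constant hazards h = −ln(1−R) and g = −ln(1−D). The expected crude percentage is

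crude = h/(h+g) × [1 − (1−R)(1−D)].

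For R = 20%, h = 0.223:

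- D = 10% (g = 0.105): 0.679 × 0.28 = 19.0%
- D = 20% (g = 0.223): 0.500 × 0.36 = 18.0%
- D = 30% (g = 0.357): 0.385 × 0.44 = 16.9%

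With R = D = 20%, that is 30 × 0.18 = 5.4 expected patients with an event instead of 30 × 0.20 = 6.0. The timing assumption matters. If all dropouts left at the start, the figure would be 0.80 × 20% = 16.0%. If every event came before any exit, it would stay at 20%.

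**Step 3: a zero count.** With no events the crude percentage and the Kaplan-Meier estimate are both 0%, whatever the dropout. Only the upper limit changes. Using patients followed through 12 months, 1 − 0.025^(1/n) gives 12.8% for 0/27, 14.2% for 0/24 and 16.1% for 0/21 (3, 6 and 9 of 30 lost, assumed).

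**The case against.** The best defence is that this is a declared feasibility study. The protocol's statistical section is descriptive, no endpoint is powered, no safety threshold has to be met, and SAP 4.8 excludes inferential testing of safety data. Stopping rules and the interim review rest on individual events, not on this percentage. Given a count and an N, any reader can compute an exact interval. Exits will be visible in Tables 14.1.1 and 14.1.2, and events are split by period.

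Most of this is fair, and it limits the weight of the point without removing it. An interval around one proportion tests nothing and needs no power. A reader can compute it only if N is defined, and it is not. The disposition tables are not linked to the primary result.

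Two stronger readings are tempting, and the documents do not support them:

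- **A reader might infer that the SAP rules early dropouts to be event-free.** It says no such thing. An all-treated population with no imputation points that way, but the use of available data and the unexplained N in each column leave the denominator open.
- **A reader might infer that the percentage errs in the reassuring direction whenever anyone leaves.** It does not. A zero count is unaffected, and so is the count when a patient leaves after already having an event.

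Constant hazards also suit this composite only loosely. Pneumothorax counts within 2 days and pneumonia within 7 days of a procedure, when few patients will have left, so the Step 2 figures may overstate the bias.

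**Conclusion.** The point holds in two parts. The larger is the missing interval: with at most 30 patients, zero events leaves true risks of up to 11.6% open, and three events leaves 2.1% to 26.5%. This needs no assumption beyond n = 30 with complete follow-up.

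The smaller is the undefined 12-month N. If N is all treated patients, a non-zero incidence is understated by about 1 to 3 percentage points at a true risk of 20% with 10% to 30% dropout. That rests on assumed dropout and constant hazards, and it lies well inside sampling error.

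Severity is modest: no decision rule in the plan turns on this figure. The change is still worthwhile because it concerns the primary result and needs no new data.

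**What to change.** In SAP 4.8.1 and the 12-month total column of Table 14.3.1:

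1. Label the blank Total row as patients with any serious adverse event of interest.
2. Define N as all treated patients. Protocol 8.3 instead puts everyone who entered the treatment room at Visit 2 in the Safety Population, so the two documents should be reconciled at the same time.
3. Keep the count and percent, and add the exact (Clopper-Pearson) 95% interval for the composite. Intervals for the components are optional.
4. As a supplement, report the Kaplan-Meier cumulative incidence of the composite. Time zero is Bronchial Rheoplasty 1, follow-up runs through 12 months after Rheoplasty 2 as in the table, and patients are censored at last contact. Death is a component, so it is not a competing risk. Protocol 7.2.4 places the second procedure 3 to 6 weeks after the first, so windows run from about 365 + 21 = 386 to 365 + 42 = 407 days. State in advance the day at which the curve is read, and the end of the window for patients with one procedure only.
5. If there are no events, the usual Kaplan-Meier interval has no width. Report instead the exact upper limit for all treated patients and for those followed through 12 months (for example, 11.6% for 0/30 and 14.2% for 0/24).

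The cost is a few table entries, a footnote and a slightly less favourable safety figure. The study stays descriptive, and SAP 4.8 need not change.
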